9.2. Quality of Life in Epilepsy – 31 (QOLIE-31)

Table 13:QOLIE-31 Scoring Form

			Re	sponse			-		
Scale Question	1	2	3	4	5	6	Subtotal		Final Scale Score (0-100) (Domain Score)
A. Energy (tiredness)									
How much of the time during the past 4 weeks									
Did you feel full of pep? ¹	100	80	60	40	20	0		-	
Did you have a lot of energy? ¹	100	80	60	40	20	0			
Did you feel worn out? ¹	0	20	40	60	80	100		•	
Did you feel tired? ¹	0	20	40	60	80	100		-	
						TOTAL:		÷4=	
How much do the above problems and worries about energy distress you overall? ⁹	100%	75%	50%	25%	10%			-	
B. Emotions (mood)									
How much of the time during the past 4 weeks								_	
Have you been a very nervous person? ¹	0	20	40	60	80	100		-	
Have you felt so down in the dumps that nothing could cheer you up? ¹	0	20	40	60	80	100		-	
Have you felt calm and peaceful? ¹	100	80	60	40	20	0			
Have you felt downhearted and blue? ¹	0	20	40	60	80	100		-	
Have you been a happy person? ¹	100	80	60	40	20	0		•	
						TOTAL			

			Re	sponse			_		
Scale Question	1	2	3	4	5	6	Subtotal		Final Scale Score (0-100) (Domain Score)
How much do the above problems and worries about energy distress you overall? ⁹	100%	75%	50%	25%	10%				
C. Daily Activities (work, drive, social)									
How much of the time during the past 4 weeks									
Has your health limited your social activities (such as visiting with friends or close relatives)? ¹	0	20	40	60	80	100		-	
How much of the time during the past 4 weeks your epilepsy or antiepileptic medication has caused trouble with								_	
Leisure activities (such as hobbies, going out)? ²	0	25	50	75	100			-	
Driving (or transportation)? ²	0	25	50	75	100			-	
How much do your work limitations bother you? ³	100	75	50	25	0			-	
How much do your social limitations bother you? ³	100	75	50	25	0			-	
						TOTAL:		- ÷5=	
How much do the above problems and worries about energy distress you overall? ⁹	100%	75%	50%	25%	10%			-	

Image: Second contraction Second c				Re	sponse			-		

Trouble remembering things people tell you?1020406080100Trouble concentrating on reading?1020406080100Trouble concentrating on doing one thing at a time?1020406080100How much do your memory difficulties bother you?31007550250How much do the above problems and worries about $\div 6 = $ $\div 6 = $ $\bullet = $ $\bullet = $		0	33.3	66.7	100				-	
Trouble concentrating on reading?1020406080100Trouble concentrating on doing one thing at a time?1020406080100How much do your memory difficulties bother you?31007550250TOTAL: $\div 6 =$	In the past 4 weeks, how often have you had									
Trouble concentrating on doing one thing at a time? ¹ 0 20 40 60 80 100 How much do your memory difficulties bother you? ³ 100 75 50 25 0 How much do the above problems and worries about TOTAL: $\div 6 =$ $\div 6 =$ $\rightarrow 6 =$	Trouble remembering things people tell you? ¹	0	20	40	60	80	100		-	
How much do your memory difficulties bother you? ³ How much do the above problems and worries about $100 75 50 25 0 $ $TOTAL: $ $\div 6 = $	Trouble concentrating on reading? ¹	0	20	40	60	80	100		_	
How much do the above problems and worries about TOTAL: $\div 6 =$	Trouble concentrating on doing one thing at a time? ¹	0	20	40	60	80	100		-	
How much do the above problems and worries about	How much do your memory difficulties bother you? ³	100	75	50	25	0			-	
		100%	75%	50%	25%	10%	TOTAL:		÷6=	
		100%	75%	50%	25%	10%				

			Re	sponse			_		
Scale Question	1	2	3	4	5	6	Subtotal		Final Scale Score (0-100) (Domain Score)
E. Medication Effects (physical, mental)									
During the past 4 weeks									
How much do physical effects of antiepileptic medication bother you? ³	100	75	50	25	0				
How much do mentals effects of antiepileptic medication bother you? ³	100	75	50	25	0			-	
How worried are you that medications you are taking will be bad for you if taken for a long time? ⁵	0	33.3	66.7	100	0			_	
						TOTAL:		÷ 3 =	
How much do the above problems and worries about energy distress you overall? ⁹	100%	75%	50%	25%	10%			-	
F. Seizure Worry (impact of seizures)									
How much of the time during the past 4 weeks									
Have you worried about having another seizure? ¹	0	20	40	60	80	100			
How fearful are you of having a seizure during the next month? ⁶	0	33.3	66.7	100				-	
Do you worry about hurting yourself during a seizure? ⁷	0	50	100					-	
How worried are you about embarrassment or other social problems resulting from having a seizure during the next month? ⁵	0	33.3	66.7	100				-	
How much do your seizures bother you? ³	100	75	50	25	0			-	
How much do the above problems and worries about energy distress you overall? ⁹	100%	75%	50%	25%	10%	TOTAL:		÷ 5 =	

			Re	sponse			-	
Scale Question	1	2	3	4	5	6	Subtotal	Final Scale Score (0-100) (Domain Score)
G. Overall Quality of Life Overall, how would you rate your quality of life? (10 = Best Possible Quality of Life; 0 = Worst Possible Quality of Life)	(multip	ly respor	nse by 10)				
How has the quality of life been during the past 4 weeks? ⁸	100	75	50	25	0			
How much does the state of your quality of life distress you overall? ⁹	100%	75%	50%	25%	10%	TOTAL:		÷ 2 =

Note: The total number of items in each scale is listed as the divisor for each subtotal. However, due to missing data, the divisor might actually be less than that as noted. The divisor should be the number of items that the respondent answered within the scale.

¹1=All of the time, 2=Most of the time, 3=A good bit of the time, 4=Some of the time, 5=A little of the time, 6=None of the time

²1=A great deal, 2=A lot, 3=Somewhat, 4=Only a little, 5=Not at all

 $^{3}1$ = Not at all bothersome and 5 = Extremely bothersome

⁴1= Yes, a great deal, 2=Yes, somewhat, 3=Only a little, 4=No, not at all

⁵1=Very worried, 2=Somewhat worried, 3=Not very worried, 4=Not at all worried

⁶1=Very fearful, 2=Somewhat fearful, 3=Not very fearful, 4=Not fearful at all

⁷1=Worry a lot, 2=Occasionally worry, 3=Don't worry at all

⁸1=Very well: could hardly be better, 2=Pretty good, 3=Good and bad parts about equal, 4=Pretty bad, 5=Very bad: could hardly be worse

⁹1=Not at all, 2=Somewhat, 3=Moderately, 4=A lot, 5=Very Much

A QOLIE-31 overall score is obtained using a weighted average of the multi-item scale scores found in the table below (Table 15). If a value for Final Scale Score or Distress Score % is missing, the Weighted Subtotal cannot be calculated. However, if the Distress Score % is available, it can be used for the Sum Distress

QOLIE-31 Scale	Final Scale Score (Domain Score)	Distress Score %		Weighted Subtotal
A. Energy	X		=	
B. Emotions	X		=	
C. Daily Activities	X		=	
D. Mental Activity	X		=	
E. Medication Effects	X		=	
F. Seizure Worry	X		=	
G. Overall QoL	X		=	
	Sum Distress=	: 	Sum Weights=	

Table 14: Formula for Calculating QOLIE-31 Overall Score

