PGI-C Score at Visits 2, 3, and 4	mITT	PGI-C score over time will be analyzed using a Mixed Model for Repeated Measures (MMRM) analysis. Treatment group (CVL-865 7.5 mg, CVL-865 25 mg, or placebo), visit, and the interaction between treatment group and visit will be included as fixed factors in the MMRM. Subject will be included as a random effect, and an unstructured covariance structure will be used for the repeated measures. The difference between each CVL-865 level versus placebo at each visit will be estimated based on the LSMeans from the MMRM.
CGI-S Score - Change from Baseline to Visits 2, 3, and 4	mITT	Change from baseline in CGI-S score over time will be analyzed using similar MMRM model as described above for PGI-C score.
CGI-I Score at Visit 2, 3, and 4	mITT	CGI-S score over time will be analyzed using similar MMRM model as described above for PGI-C score.
QOLIE-31 Overall and Domain Score - Change from Baseline to Visit 4	mITT	Changes from baseline in QOLIE-31 Overall Scores will be compared using an ANCOVA model with the baseline score as a covariate and treatment group included in the model as fixed effects in the mITT population. This estimand will include available post-baseline response data that occur before discontinuation of treatment or addition of rescue medication. The differences between each treatment dose group and placebo will be estimated based on the LSMeans difference between each CVL-865 dose group and placebo with corresponding 90% CI. The QOLIE-31 Domain Scores will be analyzed the same way, by each of the following categories: Energy, Emotions, Daily

Endpoint	Analysis Population	Analysis Method
		Activities, Mental Activity, Medication Effects, Seizure Worry, and Overall Quality of Life.
HUI Utility Score - Change from Baseline to Visit 4	mITT	Overall Health-Related Quality of Life (HRQL) Utility Scores (HUI-3 and HUI-2) will be analyzed using an ANCOVA model as described above for QOLIE-31 Overall Scores.

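### If a QOLIE-31 domain has no score, SAP 9.2 lets its distress weight stay in Sum Distress; read literally, this scores the domain as zero at that visit

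*SAP*

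**What the plan says.** SAP 9.2 defines the overall score in words: "A QOLIE-31 overall score is obtained using a weighted average of the multi-item scale scores found in the table below". The table meant is Table 14. For each of seven domains it has a domain score, a distress percentage and their product, the weighted subtotal. It ends with two totals: Sum Distress for the percentages and Sum Weights for the subtotals.

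Two sentences in SAP 9.2 deal with a missing component. The first says: "If a value for Final Scale Score or Distress Score % is missing, the Weighted Subtotal cannot be calculated". The second says: "However, if the Distress Score % is available, it can be used for the Sum Distress".

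Missing items within a domain are handled separately, in the note under Table 13: "The divisor should be the number of items that the respondent answered within the scale".

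The score is then used in SAP 5.11.1, Table 11, for the change to Visit 4: "Changes from baseline in QOLIE-31 Overall Scores will be compared using an ANCOVA model with the baseline score as a covariate". That entry adds no rule for a missing domain.

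**The concern.** A weighted average needs the same components above and below the line. Here a domain without a score contributes nothing to the sum of subtotals, while its weight may still be counted in the sum of weights. On a scale headed "Final Scale Score (0-100"), that gives the domain the worst possible value.

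This also departs from the SAP's own practice. At item level the divisor shrinks to the items answered. For the Health Utilities Index, SAP 9.3 computes the overall utility only for subjects whose questionnaire has no missing data. The QOLIE-31 overall score has neither protection at domain level.

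What is at stake is the value of a named secondary endpoint for the subjects concerned. If a domain is blank at one of the two visits only, the subject shows a change from baseline that comes from the scoring rule.

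**Working it through.** The plan gives no numerical QOLIE-31 result to reproduce, so the check applies the Table 14 arithmetic directly.

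**Inputs**

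- Seven domains with scores s from 0 to 100 (SAP 9.2, Table 13).
- Distress weights w of 100%, 75%, 50%, 25% or 10% for responses 1 to 5 (SAP 9.2, Table 13).
- Overall score = Sum Weights / Sum Distress. This is inferred from the term weighted average and the two totals in Table 14.
- Illustrative domain scores of 60. This is an assumption, because the documents give no expected values.

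**Formulas**, with domain k unscored and W the sum of all seven weights:

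- Weight kept: A = (sum of s × w over the six scored domains) / W.
- Weight dropped: B = (the same sum) / (W − w_k).
- Domain entered as zero: Z = (the same sum + 0 × w_k) / W, which equals A exactly.
- Relative loss: 1 − A/B = w_k / W. This does not depend on the domain scores.
- Shortfall against the score the subject would have had with complete data: s_k × w_k / W, which is never negative.

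**Equal weights, all observed domains 60**

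- A = 60 × 6/7 = 51.43.
- B = 60.00.
- Loss = 8.57 points, or 1/7 = 14.3%.

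**Missing domain weighted 100%, the other six 50%**

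- A = (60 × 6 × 0.5) / (6 × 0.5 + 1.0) = 180/4 = 45.0.
- B = 60.0.
- Loss = 25%.

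**Limits over the permitted weights**

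- Smallest: missing domain 10%, others 100%: 0.1/6.1 = 1.6%.
- Largest: missing domain 100%, others 10%: 1.0/1.6 = 62.5%.

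**Mixed example (also assumed).** In the Table 14 order of domains, the scores are 55, 60, 65, 50, 45, 40, 70 and the weights 50%, 50%, 75%, 25%, 50%, 25%, 75%. The complete score is 203.75/3.5 = 58.21.

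| Unscored domain | Weight kept | Weight dropped |
|---|---|---|
| Energy | 50.36 | 58.75 |
| Emotions | 49.64 | 57.92 |
| Daily Activities | 44.29 | 56.36 |
| Mental Activity | 54.64 | 58.85 |
| Medication Effects | 51.79 | 60.42 |
| Seizure Worry | 55.36 | 59.62 |
| Overall QoL | 43.21 | 55.00 |

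Keeping the weight gives 43.21 to 55.36, always below 58.21. Dropping it gives 55.00 to 60.42, on either side of 58.21.

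**Effect on the endpoint.** Take the equal-weight case with a true score of 60 at both visits.

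- Domain blank at Visit 4 only: 51.43 − 60 = −8.57, a false decline.
- Domain blank at baseline only: 60 − 51.43 = +8.57, a false improvement. The baseline covariate is also too low.
- Blank at both visits: 51.43 − 51.43 = 0, so the errors cancel in this example.

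**When it happens.** Because the item-level divisor adjusts, a domain is unscored only if all its scored items are blank. Table 13 shows from two items (Overall Quality of Life) to six (Mental Activity), with three for Medication Effects. The distress item must also be answered. If it is blank too, the domain drops out of both totals and no zero is implied.

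**The case against.** Four points can be made for the plan as it stands.

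- **The denominator is inferred.** Table 14 is captioned as a formula, but the text reviewed shows two totals and no division, and the sentence about Sum Distress runs straight into a broken table. A printed formula may have been lost in reading the file. This stands as a limit on certainty. Even so, a weighted average with those two totals leaves little room for another divisor.
- **The wording is permissive.** The SAP says the weight can be used, not that it must be, and it does not say that an overall score is produced when a subtotal is absent. A reader might infer that the SAP requires the missing domain to count against the subject; the text does not go that far. If the overall score were set to missing in this case, no error would arise. But the sentence allowing the weight would then serve little purpose, and the choice is left to the programmer.
- **The trigger is narrow.** Partial non-response is already handled, and two conditions must hold together. This stands in full.
- **The importance is limited.** The endpoint is one of seven other secondary efficacy endpoints, in a trial that SAP 5.4 calls exploratory and leaves without multiplicity adjustment. This stands as well.

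A reader might also infer that the error always runs in one direction and so biases the treatment comparison. The documents do not support that. The direction is fixed only for a single visit's score. For change from baseline it depends on which visit has the gap, and nothing in the documents indicates that such gaps differ between arms.

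**Conclusion.** The point holds as a defect in a stated scoring rule. Taken literally, and with Sum Distress as the divisor, SAP 9.2 scores an unscored domain as zero whenever its distress item was answered. That visit's overall score is then too low by w_k / W relative to the average over the scored domains: 14.3% with equal weights, and between 1.6% and 62.5% over the permitted weights. The point values (51.4 or 45.0 instead of 60) rest on the assumed scores of 60 and the chosen weights; the percentages do not depend on the scores.

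What is shown is error in individual scores for what should be few subjects. No effect on the difference between arms has been shown or estimated. The domain-score analyses and the primary and key secondary endpoints are untouched. It is worth correcting because the text is open to a reading that gives a wrong value, and the correction is trivial.

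**What to change.** In SAP 9.2, replace the permissive sentence with a rule that a domain's distress percentage enters Sum Distress only when that domain's weighted subtotal exists, so that both totals cover the same domains. Print the division under Table 14: overall score = Sum Weights / Sum Distress. If the sponsor instead intends the overall score to be missing when a subtotal is missing, the SAP should say so.

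Requiring a minimum number of scored domains is a matter of preference and is not needed to remove the error.

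The cost is one sentence and one printed formula, with no change to data collection or sample size. The same edit can correct the cross-reference, which points to Table 15 although the formula table is Table 14.

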9.3. Health Utilities Index (HUI)

HUI Utility Score

The HUI is a rating scale used to measure general health status and health-related quality of life. The HUI questionnaires are designed to map onto 2 classification systems, HUI-2 and HUI-3, capable of measuring 24,000 and 972,000 unique health states, respectively. The HUI classifications measure a range of health domains with examples including sensation, mobility, pain, cognition, ambulation, and emotion. The HUI-3 health status classification system evolved from applications of the HUI-2 system and is considered to be complementary to the HUI-2 health status classification system. They both provide a descriptive measure of ability or disability for each subject on each HUI-2 and HUI-3 attribute, as well as a composite description of overall health status according to both systems.

The 15-item family of questionnaires for self-completion have been designed to collect the minimum amount of information required to classify subjects' health status according to both the HUI-2 and HUI-3 classification systems. The standard HUI 15-item questionnaires for self-completion are as follows:

- 1. Which one of the following best describes your ability, during the past week, to see well enough to read ordinary newsprint?
 - a) Able to see well enough without glasses or contact lenses
 - b) Able to see well enough with glasses or contact lenses
 - c) Unable to see well enough even with glasses or contact lenses
 - d) Unable to see at all
- 2. Which one of the following best describes your ability, during the past week, to see well enough to recognize a friend on the other side of the street?
 - a) Able to see well enough without glasses or contact lenses
 - b) Able to see well enough with glasses or contact lenses
 - c) Unable to see well enough even with glasses or contact lenses
 - d) Unable to see at all
- 3. Which one of the following best describes your ability, during the past week, to hear what was said in a group conversation with at least three other people?
 - a) Able to hear what was said without a hearing aid
 - b) Able to hear what was said without a hearing aid
 - c) Unable to hear what was said even with a hearing aid
 - d) Unable to hear what was said, but did not wear a hearing aid
 - e) Unable to hear at all
- 4. Which one of the following best describes your ability, during the past week, to hear what was said in a conversation with one other person in a quiet room?
 - a) Able to hear what was said without a hearing aid
 - b) Able to hear what was said without a hearing aid
 - c) Unable to hear what was said even with a hearing aid
 - d) Unable to hear what was said, but did not wear a hearing aid
 - e) Unable to hear at all

- 5. Which one of the following best describes your ability, during the past week, to be understood when speaking your own language with people who do not know you?
 - a) Able to be understood completely
 - b) Able to be understood partially
 - c) Unable to be understood
 - d) Unable to speak at all
- 6. Which one of the following best describes your ability, during the past week, to be understood when speaking with people who know you well?
 - a) Able to be understood completely
 - b) Able to be understood partially
 - c) Unable to be understood
 - d) Unable to speak at all
- 7. Which one of the following best describes how you have been feeling during the past week?
 - a) Happy and interested in life
 - b) Somewhat happy
 - c) Somewhat unhappy
 - d) Very unhappy
 - e) So unhappy that life was not worthwhile
- 8. Which one of the following best describes the pain and discomfort you have experienced during the past week?
 - a) Mild to moderate pain or discomfort that prevented no activities
 - b) Moderate pain or discomfort that prevented no activities
 - c) Moderate to severe pain or discomfort that prevented no activities
 - d) Severe pain or discomfort that prevented most activities
- 9. Which one of the following best describes your ability, during the past week, to walk? Note: Walking equipment refers to mechanical supports such as braces, a cane, crutches or a walker.
 - a) Able to walk around the neighborhood without difficulty, and without walking equipment.
 - b) Able to walk around the neighborhood with difficulty; but did not require walking equipment or the help of another person
 - c) Able to walk around the neighborhood with walking equipment, but without the help of another person
 - d) Able to walk only short distances with walking equipment, and required a wheelchair to get around the neighborhood
 - e) Unable to walk alone, even with walking equipment.
 - f) Able to walk short distances with the help of another person, and required a wheelchair to get around the neighborhood
 - g) Unable to walk at all

10. Which one of the following best describes your ability, during the past week, to use your hands and fingers?

Note: Special tools refers to hooks for buttoning clothes, gripping devices for opening jars or lifting small items, and other devices to compensate for limitations of hands or fingers.

- a) Full use of two hands and ten fingers
- b) Limitations in the use of hands or fingers, but did not require special tools or the help of another person
- c) Limitations in the use of hands or fingers, independent with use of special tools (did not require the help of another person)
- d) Limitations in the use of hands or fingers, required the help of another person for some tasks (not independent even with use of special tools)
- e) Limitations in the use of hands or fingers, required the help of another person for most tasks (not independent even with use of special tools)
- f) Limitations in the use of hands or fingers, required the help of another person for all tasks (not independent even with use of special tools)
- 11. Which one of the following best describes your ability, during the past week, to remember things?
 - a) Able to remember most things
 - b) Somewhat forgetful
 - c) Very forgetful
 - d) Unable to remember anything at all
- 12. Which one of the following best describes your ability, during the past week, to think and solve day to day problems?
 - a) Able to think clearly and solve day to day problems
 - b) Had a little difficulty when trying to think and solve day to day problems.
 - c) Had some difficulty when trying to think and solve day to day problems.
 - d) Had a great difficulty when trying to think and solve day to day problems.
 - e) Unable to think or solve day to day problems.
- 13. Which one of the following best describes your ability, during the past week, to perform basic activities?
 - a) Eat, bathe, dress and use the toilet normally
 - b) Eat, bathe, dress or use the toilet independently with difficulty
 - c) Required mechanical equipment to eat, bathe, dress or use the toilet independently
 - d) Required the help of another person to eat, bathe, dress or use the toilet
- 14. Which one of the following best describes how you have been feeling during the past week?
 - a) Generally happy and free from worry
 - b) Occasionally fretful, angry, irritable, anxious or depressed
 - c) Often fretful, angry, irritable, anxious or depressed
 - d) Almost always fretful, angry, irritable, anxious or depressed
 - e) Extremely fretful, angry, irritable, anxious or depressed; to the point of needing professional help

- 15. Which one of the following best describes the pain or discomfort you have experienced during the past week?
 - a) Free of pain and discomfort.
 - b) Occasional pain or discomfort. Discomfort relieved by non-prescription drugs or selfcontrol activity without disruption of normal activities.
 - c) Frequent pain or discomfort. Discomfort relieved by oral medicines with occasional disruption of normal activities
 - d) Frequent pain or discomfort; frequent disruption of normal activities Discomfort required prescription narcotics for relief.
 - e) Severe pain or discomfort. Pain not relieved by drugs and constantly disrupted normal activities.
- 16. Overall, how would you rate your health during the past week?
 - a) Excellent
 - b) Very good
 - c) Good
- 17. How did you complete the questionnaire? Please select the one answer that best describes your situation
 - a) By myself, without any help from anyone else
 - b) By myself, except someone else circled the answers on the questionnaire form for me
 - c) With the help of someone else
 - d) This questionnaire was completed by a family member, without help from the subject or patient
 - e) This questionnaire was completed by a nurse or other health professional, without help from the subject or patient
 - f) This questionnaire was completed by another person, without help from the subject or patient

Self-Complete HUI-3 HUI-2 Question # Attribute Attribute 1 Vision -2 3 → Hearing
 Sensation Δ 5 Speech 6 7 Emotion 8 Pain 9 → Ambulation
→ ✤ Mobility 10 → Dexterity _-11 ➡ Cognition Cognition 12 13 → Self-Care 14 Emotion 15 Pain

The mappings of the self-complete questions to the HUI-3 and HUI-2 attribute levels are as follows:

From the standard HUI 15-item questionnaire data we are able to determine 8 scores (with differing number of variables in the scoring) which are used to calculate an overall utility score for HUI-3 and HUI-2:

- 1. HUI-3 attribute levels (8 variables; calculated from HUI 15-item questionnaire data)
- 2. HUI-3 single-attribute utility scores (8 variables; calculated from the HUI-3 attribute levels)
- 3. HUI-3 comprehensive health state (1 variable; 8-element vector from HUI-3 attribute levels)
- 4. HUI-3 overall multi-attribute utility score (1 variable; calculated from single-attribute utility scores)
- 5. HUI-2 attribute levels (7 variables; calculated from the HUI-3 attribute levels)
- 6. HUI-2 single-attribute utility scores (7 variables; calculated from the HUI-2 attribute levels)
- 7. HUI-2 comprehensive health state (1 variable; 7-element vector from HUI-3 attribute levels)
- 8. HUI-2 overall multi-attribute utility score (1 variable; calculated from single-attribute utility scores)

The statistical analysis will be completed utilizing the **OVERALL MULTI-ATTRIUBUTE UTILITY SCORES for HUI-3 and HUI-2**.

The HUI-2 and HUI-3 multi-attribute utility score scales are each defined such that the score for dead is set to 0.00. The score for perfect health (defined as the state having all attributes at level 1) is set to 1.00. The HUI-2 multi-attribute utility scale is defined for the interval -0.03 to 1.00; the HUI-3 multi-attribute utility scale is defined for the interval -0.36 to 1.00. Negative scores represent states considered worse than dead.

The following instructions guide the user in the determination of HUI-3 and HUI-2 attribute levels and overall multi-attribute utility scores for each subject:

1. Determining HUI-3 Attribute Levels (8 variables)

The levels are Vision, Hearing, Speech, Emotion, Pain, Ambulation, Dexterity, and Cognition. Four of these attributes (vision, hearing, speech, and cognition) each require input from sets of two questions to determine the attribute level.

The scoring methods for HUI-3 Attribute Levels can be found in Tables 15-19:

Table 15:HUI-3 Vision Attribute Level Decision Table

(based on self-complete questionnaire responses)

	Question #2 Response						
Question #1 Response	a	b	C.	d			
a	1	2	3	3			
b	2	2	3	3			
с	4	4	5	5			
d	6	6	6	6			

Cerevel

(based on self-c	omplete questionna	ire responses)							
	Question #4 Response								
Question #3 Response	a	b	с	d	e				
a	1	1	1	1	1				
b	2	3	3	3	3				
с	4	5	6	6	6				
d	4	5	6	6	6				
e	6	б	б	6	б				

Table 17:HUI-3 Speech Attribute Level Decision Table

	Question #6 Response							
Question #5 Response a b c	a	b	c	d				
a	1	1	1	1				
b	2	3	5	5				
с	4	4	5	5				
d	4	4	5	5				

Table 18:HUI-3 Cognition Attribute Level Decision Table

	Question #12 Response								
Question #11 Response	a	b	с	d	e				
a	1	2	2	5	6				
b	3	4	4	5	6				
С	5	5	5	5	6				
d	6	6	6	6	6				

Table 19: Ambulation, Dexterity, Emotion and Pain Attribute Level Decision Table

(based on self-c	based on self-complete questionnaire responses)										
	Question Response										
Attribute	Question #	a	b	с	d	е	f				
Ambulation	9	1	2	3	4	5	6				
Dexterity	10	1	2	3	4	5	6				
Emotion	7	1	2	3	4	5	n/a				
Pain	8	1	2	3	4	5	n/a				

The standard, and somewhat arbitrary, HUB attribute levels for comatose study subjects are defined as follows: Vision= Level 6; Hearing= Level 6; Speech= Level 5; Ambulation= Level 6; Dexterity= Level 6; Emotion= Level 3; Cognition= Level 6; and Pain= Level 3.

2. Determining HUI-2 Attribute Levels (7 variables)

The levels are Sensation, Mobility, Cognition, Self-Care, Emotion, Pain, and Fertility. HU1-2 level codes for sensation and mobility attributes are derived directly from previously determined HUI-3 attribute level codes. Note: To distinguish clearly previously determined HUI-3 levels from HUI-2 levels being determined, the HUI-3 levels are printed as words and the HUI-2 levels are specified using numerals.

The scoring methods for HUI-2 Attribute Levels can be found in Tables 20-24:

Table 20: HUI-2 Sensation Attribute Level Decision Table

(based on levels of HUI-3 attributes of vision, hearing, and speech) **HUI-3** Levels **HUI-3** Levels of Speech Vision Hearing One Two Three Four Five One One One Two One Three One Four One Five One Six Two One Two Two Two Three Two Four Two Five Two Six Three or Four or Five One Three or Four or Five Two Three or Four or Five Three Three or Four or Five Four Three or Four or Five Five Three or Four or Five Six Six One Six Two Six Three Six Four Six Five Six Six

Table 21: HUI-2 Mobility Attribute Level Decision Table

HUI-3 Levels of	HUI-3 Levels of Dexterity								
Ambulation	One	Two	Three	Four	Five	Six			
One	1	1	1	1	1	1			
Two	2	2	2	2	2	2			
Three	3	3	3	3	3	3			
Four	3	3	3	3	3	3			
Five	4	4	4	4	4	4			
Six	4	4	4	4	4	5			

cerevel

Question #11	Question #12 Response						
Response	a	b	с	d	e		
a	1	2	2	3	4		
b	2	2	2	3	4		
с	2	3	3	3	4		
d	4	4	4	4	4		

HUI-2 Cognition Attribute Level Decision Table Table 22:

Table 23:	HUI-2 Self-Care, Emotion, and Pain Attributes Level Decision Table
-----------	--

	Question Response								
Attribute	Question #	a	b	с	d	e			
Self-Care	13	1	2	3	4	n/a			
Emotion	14	1	2	3	4	5			
Pain	15	1	2	3	4	5			

HUI-2 Fertility Attributes Level Decision Table Table 24:

The HUI2 fertility attribute level code is assumed to be level 1

The standard, and somewhat arbitrary, HUI-2 attribute levels for comatose study subjects are as follows: Sensation= Level 4; Mobility= Level 5; Emotion= Level 3; Cognition Level 4; Self-Care= Level 4; Pain= Level 3; and Fertility= Level 1.

3. Determining Single-Attribute HUI-3 Utility Scores (8 variables)

Single-attribute utility functions provide preference scores of relative desirability for functional capacity within single attributes defined by the HUI-3 health status classification system. The HUI-3 levels are labelled using integers. Each single-attribute utility function is defined on a scale from 0.00 to 1.00.

The most disabled level of an attribute has a single-attribute utility score of 0.00, and no disability of an attribute has a single-attribute utility score of 1.00.

Cerevel

Attribute	Vision	Hearing	Speech	Ambulation	Dexterity	Emotion	Cognition	Pain
Level	u_1	u ₂	u ₃	u4	u5	u ₆	u7	u ₈
1	1.00	1.00	1.00	1.00	1.00	1.00	1.00	1.00
2	0.95	0.86	0.82	0.83	0.88	0.91	0.86	0.92
3	0.73	0.71	0.67	0.67	0.73	0.73	0.92	0.77
4	0.59	0.48	0.41	0.36	0.45	0.33	0.70	0.48
5	0.38	0.32	0.00	0.16	0.20	0.00	0.32	0.00
6	0.00	0.00	n/a	0.00	0.00	n/a	0.00	n/a

Scoring is as follows:

Legend: u_x: single-attribute utility function for attribute x, n/a: not applicable

Note: The mean single-attribute utility score for level 3 cognition is greater than the mean single-attribute utility score for level 2 cognition.

4. Determining Single-Attribute HUI-2 Utility Scores (7 variables)

Single-attribute utility functions provide preference scores of relative desirability for functional capacity within single attributes defined by the HUI-2 health status classification system. The HUI-2 levels are labelled using integers. Each single-attribute utility function is defined on a scale from 0.00 to 1.00.

The lack of functional capacity, or most disabled level, in an attribute has a single-attribute utility score of 0.00, and full function, or no disability, for an attribute has a single-attribute utility score of 1.00.

Attribute	Sensation	Mobility	Emotion	Cognition	Self-Care	Pain	Fertility
Level	u_1	u_2	u ₃	u 4	u 5	u ₆	u 7
1	1.00	1.00	1.00	1.00	1.00	1.00	1.00
2	0.87	0.92	0.86	0.86	0.85	0.95	0.75
3	0.65	0.61	0.60	0.66	0.55	0.75	0.00
4	0.00	0.34	0.37	0.00	0.00	0.42	n/a
5	n/a	0.00	0.00	n/a	n/a	0.00	n/a

Scoring is as follows:

Legend: ux: single-attribute utility function for attribute x, n/a: not applicable

5. Determining Overall Health-Related Quality of Life (HRQL) Utility Scores Using HUI-3 Utility Function (1 variable)

To calculate the HUI-3 HRQL Utility Score, the above-determined single-attribute levels are entered into the following health utility formula or subjects who do not have missing data from the 15-item questionnaire:

U=1.371(Vison*Hearing*Speech*Ambulation*Dexterity*Emotion*Cognition*Pain)-0.371

HUI-3 allows for negative scores of HRQL that represent health states considered worse than dead. The lowest possible HUI-3 score is -0.3. Note that the overall HRQL utility score for deceased subjects cannot be calculated using the HUB multi-attribute utility function and that this variable should be assigned a score of 0.00. (Dead is an anchor state of the conventional dead=0.00 to perfect health=1.00 overall HRQL utility scale and, therefore, **the score for dead is 0.00** by definition.)

6. Determining Overall Health-Related Quality of Life (HRQL) Utility Scores Using HUI-2 Utility Function (1 variable)

To calculate the HUI-2 HRQL Utility Score, the above-determined single-attribute levels are entered into the following health utility formula **for subjects who do not have missing data from the 15-item questionnaire**:

U=1.06(Sensation*Mobility*Emotion*Cognition*Self-Care*Pain*Fertility)-0.06

HUI-2 allows for negative scores of HRQL that represent health states considered worse than dead. The lowest possible HUI-2 score is -0.03. Note that the overall HRQL utility score for deceased subjects cannot be calculated using the HUB multi-attribute utility function and that this variable should be assigned a score of 0.00. (Dead is an anchor state of the conventional dead=0.00 to perfect health=1.00 overall HRQL utility scale and, therefore, **the score for dead is 0.00** by definition.)

9.4. Columbia-Suicide Severity Rating Scale (C-SSRS) Suicidal Ideation and Suicidal Behavior Scores

The C-SSRS is comprised of 10 categories with binary responses. The 10 categories include:

Category 1 – Wish to be Dead

Category 2 – Non-specific Active Suicidal Thoughts

Category 3 – Active Suicidal Ideation with Any Methods (Not Plan) without Intent to Act

Category 4 – Active Suicidal Ideation with Some Intent to Act, without Specific Plan

Category 5 – Active Suicidal Ideation with Specific Plan and Intent

Category 6 – Preparatory Acts or Behavior

Category 7 – Aborted Attempt

Category 8 – Interrupted Attempt

Category 9 – Actual Attempt (non-fatal)

Category 10 – Completed Suicide

Categories 1-5 represent Suicidal Ideation and categories 6-10 represent Suicidal Behavior. Each category is scored as 1 if there is a positive response in the category and a 0 if there are no positive responses in the category.

• Self-Injurious Behavior Without Suicidal Intent During Treatment

A subject will be categorized as having self-injurious behavior without suicidal intent if there is an occurrence of non-suicidal self-injurious behavior on the C-SSRS – Since Last Visit eCRF at any post-baseline visit.

• Baseline C-SSRS Score

Baseline represents the pre-treatment assessment of recent history, with elements of suicidal ideation assessed over the prior 6 months and elements of suicidal behavior assessed over the prior 2 years. It is scaled from 0 (no suicidal ideation or behavior) to 10 (completed suicide)

• Treatment-Emergent Suicide-Related Event

A subject will be categorized as having a treatment-emergent suicide-related event if at least one post-baseline suicidal ideation or suicidal behavior score is greater than 0.

• Treatment-Emergent Suicidal Ideation Compared to Recent History

A subject will be categorized as having treatment-emergent suicidal ideation compared to recent history when there is at least one post-baseline suicidal ideation score > 0 and is an increase from baseline. Lifetime scores are not considered for baseline suicidal ideation responses.

• Treatment-Emergent Serious Suicidal Ideation Compared to Recent History

A subject will be categorized as having treatment-emergent serious suicidal ideation compared to recent history if the baseline score was < 4 and the post-baseline suicidal ideation score increases to 4 or 5. Lifetime scores are not considered for baseline suicidal ideation responses.

• Emergence of Serious Suicidal Ideation Compared to Recent History

A subject will be categorized as having emergence of serious suicidal ideation compared to recent history if baseline score was 0 (no suicidal ideation) and post-baseline C-SSRS suicidal ideation score is either 4 or 5. Lifetime scores are not considered for baseline suicidal ideation responses.

• Emergence of Suicidal Behavior Compared to all Prior History

A subject will be categorized as having emergence of suicidal behavior compared to all prior history if there had been no suicidal behavior in Categories 6-10 reported at any pre-treatment assessment, including responses to lifetime history questions, and there is at least one positive post-baseline C-SSRS assessment in Categories 6-10. 'All Prior History' represents lifetime history.

